- E. Duration of headache lasting 2 hours or longer on a calendar day unless an acute, migraine-specific medication (i.e., triptan or ergot derivative) was used after the start of the headache, in which case no minimum duration will be specified

Health Outcome Measures:

- Change from baseline in Migraine-Specific Quality-of-Life Questionnaire, version 2.1 (MSQ v2.1)
- Change from baseline in Patient Health Questionnaire (PHQ-9)
- Change from baseline in Work Productivity and Activity Impairment Questionnaire:Migraine v2.0 (WPAI:MIGRAINE)
- Patient Satisfaction with Study Medications (PSSM)
- Patient Global Impression of Change (PGIC)
- Change from baseline in Generalized Anxiety Disorder-7 (GAD-7)
- Change from baseline in PROMIS v2.0 Cognitive Function Abilities Short-Form 6a

All efficacy analyses will be performed using the modified intention-to-treat (mITT) population, consisting of participants who receive at least 1 dose of study intervention (atogepant), have an

evaluable baseline period of eDiary data and have at least 1 evaluable postbaseline 4-week period of eDiary data.

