3.2 Efficacy Endpoints

All efficacy endpoints are exploratory. The definitions of the efficacy measures based on the eDiary data can be found in [Appendix B](#).

- Achievement of $\geq 25\%$, $\geq 30\%$, $\geq 50\%$, $\geq 75\%$, and 100% reduction in mean monthly migraine days across Weeks 1 to 12, Weeks 13 to 24, and at each 4-week interval
- Change from baseline in monthly migraine days across Weeks 1 to 12, Weeks 13 to 24, and at each monthly period
- Change from baseline in monthly headache days across Weeks 1 to 12, Weeks 13 to 24, and at each monthly period
- Change from baseline in monthly moderate or severe headache days across Weeks 1 to 12, Weeks 13 to 24, and at each monthly period
- Change from baseline in monthly cumulative hours of headache across Weeks 1 to 12, Weeks 13 to 24, and at each monthly period

- Change from baseline in monthly acute medication use days across Weeks 1 to 12, Weeks 13 to 24, and at each monthly period
- Change from baseline in monthly headache free days across Weeks 1 to 12, Weeks 13 to 24, and at each monthly period
- Change from baseline in monthly complete migraine symptom-free days across Weeks 1 to 12, Weeks 13 to 24, and at each monthly period
- Change from baseline in monthly cardinal migraine symptom-free days across Weeks 1 to 12, Weeks 13 to 24, and at each monthly period
- Achievement of $\geq 25\%$, $\geq 30\%$, $\geq 50\%$, $\geq 75\%$, and 100% reduction in mean monthly complete migraine symptom-free days across Weeks 1 to 12, Weeks 13 to 24, and at each 4-week interval
- Achievement of $\geq 25\%$, $\geq 30\%$, $\geq 50\%$, $\geq 75\%$, and 100% reduction in mean monthly cardinal migraine symptom-free days across Weeks 1 to 12, Weeks 13 to 24, and at each 4-week interval
- Change from baseline in monthly days with an individual non-headache symptom for each of the 5 most common non-headache symptoms (including difficulty with concentration and thinking clearly collected from AIM-D items 10 and 11) and cardinal individual non-headache symptoms across Weeks 1 to 12, Weeks 13 to 24, and at each monthly period
- Change from baseline in monthly Performance of Daily Activities domain score of the AIM-D at each monthly period
- Change from baseline in monthly Physical Impairment domain score of the AIM-D at each monthly period
- Change from baseline in monthly AIM-D total score at each monthly period
- Change from baseline in monthly AIM-D Item 10 score at each monthly period

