15.1 Changes to Planned Analyses in the Protocol

There are no changes to planned analyses described in protocol.

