Appendix B. Derivation of Efficacy Endpoints Based on eDiary Data

Efficacy measures were defined as follow:

A migraine day is defined as any calendar day on which a headache occurs which meets Criteria A, B, and C OR meets Criteria D and E, as listed below, as per participant eDiary. Calendar days begin at midnight and last until 11:59 PM (23:59).

A. Headache has at least 2 of the following 4 characteristics:

- Unilateral location
- Pulsating quality
- Moderate or severe pain intensity
- Aggravated by or causing avoidance of routine physical activity (e.g., walking or climbing stairs)

B. At least one of the following:

- Nausea and/or vomiting
- Photophobia and phonophobia
- Typical aura (i.e., visual, sensory, or speech/language) accompanying or within 60 minutes before headache begins

C. Duration of headache lasting 2 hours or longer on a calendar day unless an acute, migraine-specific medication (i.e., triptan or ergot derivative) was used after the start of the headache, in which case no minimum duration will be specified.

OR

D. Any headache which fulfills 1 criterion from (1) and at least 1 criterion from (2)
OR fulfills at least 2 criteria from (1) and no criteria from (2).

1. Headache characteristics:

- Unilateral location
- Pulsating quality
- Moderate or severe pain intensity

- Aggravated by or causing avoidance of routine physical activity (e.g., walking or climbing stairs)
2. Symptoms:
 - Nausea and/or vomiting
 - Photophobia and phonophobia
 - Typical aura (i.e., visual, sensory, or speech/language) accompanying or within 60 minutes before headache begins
 1. Duration of headache lasting 2 hours or longer on a calendar day unless an acute, migraine specific medication (i.e., triptan, ergot derivative, or ditan) was used after the start of the headache, in which case no minimum duration will be specified.

A headache day is defined as any calendar day on which headache pain lasting 2 hours or longer occurs unless an acute headache medication (e.g., ibuprofen, triptan) was used after the start of the headache, in which case no minimum duration will be specified. Note that antiemetics will not be counted as an acute headache medication for headache day identification. Calendar days begin at midnight and last until 11:59 PM (23:59).

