An acute medication use day is defined as any day on which a participant reports, per eDiary, the intake of allowed medication(s) to treat an acute migraine. The allowed medications include the following categories of drugs: triptans, ergots, opioids, analgesics (including acetaminophen), NSAIDs (including aspirin), and antiemetics.

A moderate or severe headache day is defined as a headache day during which the maximum pain intensity is either moderate or severe. Headache day pain intensity is defined as the worst pain intensity on any headache day where headache pain intensity will be subjectively rated by the patient on a scale from mild to severe:

- Mild pain (1)
- Moderate pain (2)
- Severe pain (3)

Moderate/severe headache day is defined as a headache day during which the maximum pain severity is either moderate or severe. Severe headache day is defined as a headache day during which the maximum pain severity is severe.

If participants experience no headache in a day, then the corresponding pain intensity of that day will be set as missing.

A headache free day is defined as any calendar day on which does not meet the definition of a headache day.

A complete migraine symptom-free day is defined as any calendar day on which a participant reports, per eDiary, no headache and no experience of any of the following non-headache symptom(s): Nausea and/or Vomiting, Sensitivity to light, Sensitivity to sound, Dizziness, Neck pain, Tiredness, Mood change, Yawning, Thirst, Cravings, Urinary frequency, and other (Forehead/facial sweating, Abnormal shedding of tears, Nasal congestion, Eyelid swelling, and Runny nose).

A cardinal migraine symptom-free day is defined as any calendar day on which a participant reports, per eDiary, no headache and no experience of any of the following non-headache symptom(s): Nausea and/or Vomiting, Sensitivity to light, and Sensitivity to sound.

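### SAP Appendix B waives the 2-hour minimum for ditans in one migraine-day criterion but not the other, the protocol waives it in neither, and the counting of ditan-only medication days is left unsettled (low severity)

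*SAP*

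**What the plan says.** A migraine day can be reached by two routes, A+B+C or D+E. C and E set a 2-hour minimum duration and waive it when certain acute drugs were taken.

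- **Protocol 3.2, criteria C and E.** The same waiver in both: "unless an acute, migraine-specific medication (i.e., triptan or ergot derivative) was used after the start of the headache".
- **SAP Appendix B, criterion C.** Unchanged from the protocol: "migraine-specific medication (i.e., triptan or ergot derivative) was used after the start of the headache".
- **SAP Appendix B, second duration criterion (the protocol's E).** Ditan is added: "migraine specific medication (i.e., triptan, ergot derivative, or ditan) was used after the start of the headache".
- **SAP Appendix B, criterion D, first limb.** "Any headache which fulfills 1 criterion from (1) and at least 1 criterion from (2"). The second limb requires two or more headache characteristics and no symptom.
- **SAP Appendix B, acute medication use day.** The categories given are "triptans, ergots, opioids, analgesics (including acetaminophen), NSAIDs (including aspirin), and antiemetics". Ditans are not named. Protocol 5.4 allows ditans for acute treatment, on a line of their own.
- **SAP 15.1.** "There are no changes to planned analyses described in protocol".
- **SAP 3.2.** "All efficacy endpoints are exploratory".

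**The concern.** The SAP calls a ditan migraine-specific on one route to a migraine day and does not on the other, and gives no reason. The effect runs the wrong way round: the route that gains the waiver is the one for partial presentations.

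The change to E also departs from the protocol, while SAP 15.1 declares no departure. The 8-to-23-day entry criterion in protocol 5.1 rests on the protocol's definition, so the same diary can give one count at eligibility and another as the analysis baseline.

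For acute medication use days, two programmers could reasonably code a ditan-only day in opposite ways.

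Monthly migraine days and responder rates are the study's stated efficacy objective, and acute medication use days are one of the listed endpoints.

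**Working it through.** **1. The plan's own figure.** The only planning figure for an affected endpoint is the half width of about 1.8 days for change in monthly migraine days (SD 7.0, n = 60; protocol 7.7, SAP 2.4). 1.96 × 7.0/√60 = 1.77; with the t distribution on 59 degrees of freedom it is 1.81. The figure reproduces, and nothing here changes it.

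**2. Classification of short headaches treated with a ditan.** Take a headache under 2 hours, with a ditan and no triptan or ergot, and read D's first limb as exactly one characteristic.

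| Characteristics | Symptoms | Route open | Protocol | SAP as written | Ditan in both C and E |
|---|---|---|---|---|---|
| 1 | ≥ 1 | D+E | no | **yes** | yes |
| ≥ 2 | 0 | D+E | no | **yes** | yes |
| ≥ 2 | ≥ 1 | A+B+C | no | **no** | yes |
| 0, or 1 with no symptom | any / 0 | none | no | no | no |

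Rows 1 and 2 show the SAP departing from the protocol. Row 3 against rows 1 and 2 shows the conflict within the SAP: the full presentation is rejected and the partial ones are counted. With ditan in neither criterion, the result is the protocol column.

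**3. Where the rules agree.** All three rule sets were compared over 0 to 4 characteristics, 0 to 3 symptoms, both durations, and no drug, triptan, ergot or NSAID: 5 × 4 × 2 × 4 = 160 combinations without a ditan, none of which differs. With a ditan and a headache of 2 hours or more, they also agree. The migraine-day effect is therefore confined to the cell in step 2.

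**4. Eligibility against analysis baseline.** As written, the SAP can only add days to the protocol count (rows 1 and 2). Putting ditan in C as well would add row 3 and widen that gap unless the protocol definition changes too. Removing ditan from E closes it.

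**5. What one day can do.** From a baseline of 8 migraine days, 4 days is a reduction of (8 − 4)/8 = 50.0%, and 5 days is (8 − 5)/8 = 37.5%. One reclassified day can change 50% responder status for a participant near the threshold.

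**6. Size for medication days, if ditans were not counted.** The documents give no ditan-use rate, so these inputs are assumptions. Shift in the mean at one time point = share of users × ditan-only days per 28.

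- 5% of users, 4 days: 0.05 × 4 = 0.2 days (3.75 of 75 participants, 15 days in total, 15/75 = 0.2).
- Range for 2% to 20% of users and 2 to 8 days: 0.02 × 2 = 0.04 to 0.20 × 8 = 1.6 days.
- In a change score, the shift is share × (postbaseline days − baseline days). Stable use gives 0.05 × (4 − 4) = 0. The full 0.2 arises only if all the use began, or all of it stopped, after baseline.

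For migraine days no size can be computed: the documents give neither ditan use nor the share of such headaches lasting under 2 hours.

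**The case against.** **On migraine days.** If D's one criterion is read as at least one, a full A+B presentation also qualifies through D+E, and the conflict within the SAP disappears. This is possible but not the natural reading, since D states its minimums explicitly elsewhere. The departure from the protocol remains on either reading. It is fair that the affected cell is narrow: durations are summed over the calendar day, so the day's total must be under 2 hours, with no triptan or ergot taken.

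**On medication days.** A reader might infer that every ditan-only day is dropped, so that a participant who moves from a triptan to a ditan appears to use less acute medication. The documents do not establish this. The category list is introduced by *include*. Protocol 5.4 goes on to allow other analgesics, which could place a ditan within a listed class. A later rule in Appendix B counts the day once the participant confirms use and enters a medication, without naming a class. Against that, the same paragraph does not count a day when no allowed medication is listed, and the only list of those in the SAP lacks ditans. What stands is ambiguity, not proven loss.

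**On headache days.** A reader might extend the point to these, but their waiver is open-ended: "unless an acute headache medication (e.g., ibuprofen, triptan) was used after the start of the headache". They are not clearly affected.

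**On importance.** The primary objective is safety, efficacy is exploratory with nominal p-values, and there is one arm, so no between-arm comparison can be biased. This stands and sets the severity. The SAP version history does record an update to the Appendix B derivations, so change there was not wholly undisclosed, but it does not mention ditans.

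**Conclusion.** The inconsistency is real. SAP Appendix B gives ditans the duration waiver in the second criterion only, the protocol gives it in neither, and SAP 15.1 does not declare the difference. On D's natural reading, the SAP counts a short ditan-treated partial presentation and rejects a full one, and its baseline can exceed the protocol's eligibility count. Separately, ditan-only days may be counted inconsistently as acute medication use days.

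A reader might conclude that the study's main efficacy result is miscounted. The documents do not support that: no efficacy endpoint has primary status, the effect is limited to ditan users, and its size is unknown. On the assumed 5% and 4 days, the medication-day mean shifts by at most about 0.2 days at one time point, and stable use largely cancels in the change from baseline. No safety result, sample size or precision figure is touched. Severity is low. Confidence is high for the mismatch in wording, but not for any particular loss of days.

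**What to change.** 1. Use one list of migraine-specific drugs in criteria C and E of SAP Appendix B. There are two consistent choices. Leaving ditan out of both matches the current protocol. Putting ditan in both requires an entry in SAP 15.1 as a change from the protocol, with a note that the eligibility count used the protocol definition and may be lower than the analysis baseline.
2. Apply the chosen definition identically at baseline and in every postbaseline 4-week period.
3. Name ditans in the acute-medication-use-day list, so that the list agrees with protocol 5.4 and with the rule that counts a day once a medication has been entered.
4. Report how many participants took a ditan and on how many days, so that readers can see the size of the effect.

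The cost is a few words in Appendix B, possibly one entry in SAP 15.1, and a programming update. Participants already enter their acute medications in the eDiary, so no new data are needed.

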Appendix C. Definition of Adverse Events of Special Interest

The following AESIs have been identified:

- Treatment-emergent elevated ALT or AST laboratory value $\geq 3 \times \text{ULN}$.
- Potential Hy's law cases: elevated ALT or AST laboratory value that is $\geq 3 \times \text{ULN}$ and an elevated total bilirubin laboratory value that is $\geq 2 \times \text{ULN}$ and, at the same time, an alkaline phosphatase laboratory value that is $< 2 \times \text{ULN}$.

Appendix D. Potentially Clinically Significant Criteria for Safety Endpoints

The potentially clinically significant (PCS) criteria for clinical laboratory parameters are described in Table D-1, the criteria for hepatic laboratory abnormalities are described in Table D-2, the PCS criteria for vital sign findings are described in Table D-3, the PCS criteria for ECG parameters are described in Table D-4, and the Clinical Interest Criteria for ECG parameters are described in Table D-5.

Table D-1. Potentially Clinically Significant Criteria for Clinical Laboratory Parameters

Category	Parameter	SI Unit	PCS Criteria	
			PCS Low	PCS High
Chemistry	Albumin	g/L	$< 0.8 \times \text{LLN}$	$> 1.2 \times \text{ULN}$
	Alanine aminotransferase	U/L	—	$\geq 3.0 \times \text{ULN}$
	Alkaline phosphatase	U/L	—	$\geq 3.0 \times \text{ULN}$
	Aspartate aminotransferase	U/L	—	$\geq 3.0 \times \text{ULN}$
	Bicarbonate	mmol/L	$< 0.9 \times \text{LLN}$	$> 1.1 \times \text{ULN}$
	Bilirubin, total	$\mu\text{mol/L}$	—	$\geq 1.5 \times \text{ULN}$
	Blood urea nitrogen	mmol/L	—	$> 1.5 \times \text{ULN}$
	Calcium	mmol/L	$< 0.9 \times \text{LLN}$	$> 1.1 \times \text{ULN}$
	Chloride	mmol/L	$< 0.9 \times \text{LLN}$	$> 1.1 \times \text{ULN}$
	Cholesterol, total	mmol/L	—	$> 1.6 \times \text{ULN}$
	Creatinine	$\mu\text{mol/L}$	—	$> 1.5 \times \text{ULN}$
	Creatine kinase	U/L	—	$> 2.0 \times \text{ULN}$
	Estimated glomerular filtration rate	mL/sec/1.73m^2	< 1	—
	Glucose, nonfasting	mmol/L	$< 0.8 \times \text{LLN}$	$> 2.0 \times \text{ULN}$
	Lactate dehydrogenase (LDH)	U/L	—	$> 3.0 \times \text{ULN}$
	Phosphorus	mmol/L	$< 0.9 \times \text{LLN}$	$> 1.1 \times \text{ULN}$
	Potassium	mmol/L	$< 0.9 \times \text{LLN}$	$> 1.1 \times \text{ULN}$
	Protein, total	g/L	$< 0.9 \times \text{LLN}$	$> 1.1 \times \text{ULN}$
	Sodium	mmol/L	$< 0.9 \times \text{LLN}$	$> 1.1 \times \text{ULN}$
	Triglycerides	mmol/L	—	$> 2.0 \times \text{ULN}$
	Uric acid	$\mu\text{mol/L}$	—	$> 1.2 \times \text{ULN}$

Category	Parameter	SI Unit	PCS Criteria	
			PCS Low	PCS High
Hematology	Basophils, absolute cell count	$10^9/L$	—	$> 2.0 \times ULN$
	Eosinophils, absolute cell count	$10^9/L$	—	$> 2.0 \times ULN$
	Hematocrit	Ratio	$< 0.9 \times LLN$	$> 1.1 \times ULN$
	Hemoglobin	g/L	$< 0.9 \times LLN$	$> 1.1 \times ULN$
	Lymphocytes, absolute cell count	$10^9/L$	$< 0.7 \times LLN$	$> 1.3 \times ULN$
	Monocytes, absolute cell count	$10^9/L$	$< 0.5 \times LLN$	$> 2.0 \times ULN$
	Neutrophils, absolute cell count	$10^9/L$	$< 0.7 \times LLN$	$> 1.3 \times ULN$
	Platelet count	$10^9/L$	$< 0.5 \times LLN$	$> 1.5 \times ULN$
	Red blood cell count	$10^{12}/L$	$< 0.9 \times LLN$	$> 1.1 \times ULN$
	White blood cell count	$10^9/L$	$< 0.9 \times LLN$	$> 1.5 \times ULN$
Urinalysis	pH	pH	$< 0.9 \times LLN$	$> 1.1 \times ULN$
	Glucose	mmol/L	—	At least 1+
	Protein	g/L	—	At least 1+
	Specific gravity	—	—	$> 1.1 \times ULN$

LLN = lower limit of normal value; ULN = upper limit of normal value; normal value provided by laboratory;

SI = Le Système International d'Unités (International System of Units)

Table D-2. Criteria for Hepatic Laboratory Abnormalities

Laboratory Parameter	Categories
ALT	$\geq 1 \times \text{ULN}$
	$\geq 1.5 \times \text{ULN}$
	$\geq 2 \times \text{ULN}$
	$\geq 3 \times \text{ULN}$
	$\geq 5 \times \text{ULN}$
	$\geq 10 \times \text{ULN}$
	$\geq 20 \times \text{ULN}$
AST	$\geq 1 \times \text{ULN}$
	$\geq 1.5 \times \text{ULN}$
	$\geq 2 \times \text{ULN}$
	$\geq 3 \times \text{ULN}$
	$\geq 5 \times \text{ULN}$
	$\geq 10 \times \text{ULN}$
	$\geq 20 \times \text{ULN}$
ALT or AST	$\geq 1 \times \text{ULN}$
	$\geq 1.5 \times \text{ULN}$
	$\geq 2 \times \text{ULN}$
	$\geq 3 \times \text{ULN}$
	$\geq 5 \times \text{ULN}$
	$\geq 10 \times \text{ULN}$
	$\geq 20 \times \text{ULN}$
Bilirubin Total	$\geq 1 \times \text{ULN}$
	$\geq 1.5 \times \text{ULN}$
	$\geq 2 \times \text{ULN}$
	$\geq 3 \times \text{ULN}$
	$\geq 5 \times \text{ULN}$
	$\geq 10 \times \text{ULN}$
	$\geq 20 \times \text{ULN}$

Laboratory Parameter	Categories
Alkaline Phosphatase	$\geq 1 \times \text{ULN}$
	$\geq 1.5 \times \text{ULN}$
	$\geq 2 \times \text{ULN}$
	$\geq 3 \times \text{ULN}$
	$\geq 5 \times \text{ULN}$
	$\geq 10 \times \text{ULN}$
	$\geq 20 \times \text{ULN}$
Concurrent Elevations ^a	ALT or AST $\geq 3 \times \text{ULN}$ and Bilirubin Total $\geq 1.5 \times \text{ULN}$
	ALT or AST $\geq 3 \times \text{ULN}$ and Bilirubin Total $\geq 2 \times \text{ULN}$
Potential Hy's Law ^a	ALT or AST $\geq 3 \times \text{ULN}$ and Bilirubin Total $\geq 2 \times \text{ULN}$ and ALP $< 2 \times \text{ULN}$

ALT alanine aminotransferase; AST aspartate aminotransferase; TBL total bilirubin; ALP alkaline phosphatase; ULN upper limit of normal (value provided by the laboratory)

a. Elevations are from the same day.

Note: A post baseline value must be more extreme than the baseline value to be considered a potentially clinically important finding.

Vital sign values will be considered PCS if they meet both the observed value criterion and the change from baseline value criterion, if both criteria are available, or meet either the observed value criterion or the change from baseline value criterion that is detailed in the following table.

Table D-3. Potentially Clinically Significant Criteria for Vital Signs

Parameter	Flag	Criteria	
		Observed Value	Change from Baseline
Sitting systolic blood pressure, mm Hg	High	≥ 180	Increase of ≥ 20
	Low	≤ 90	Decrease of ≥ 20
Sitting diastolic blood pressure, mm Hg	High	≥ 105	Increase of ≥ 15
	Low	≤ 50	Decrease of ≥ 15
Sitting Pulse rate, bpm	High	≥ 120	Increase of ≥ 15
	Low	≤ 50	Decrease of ≥ 15
Weight, kg	High	—	Increase of $\geq 7\%$
	Low	—	Decrease of $\geq 7\%$

bpm beats per minute; kg kilogram; mmHg millimeters of mercury

ECG parameter values are considered PCS if ECG values meet either the actual value or change from baseline PCS high criteria listed in the following table.

Table D-4. Potentially Clinically Significant Criteria for ECG Parameters

Parameter	Unit	Actual Value	Change from Baseline
QRS interval	msec	≥ 150	—
PR interval	msec	≥ 250	—
QTcF	msec	> 500	Increase > 60

QTc QT interval corrected for heart rate; QTcF QT interval corrected for heart rate using the Fridericia formula.

To evaluate ECG postbaseline values of clinical interest, the number and percentage of participants will be tabulated, if ECG values meet either the actual value or change from baseline criteria listed in the following table.

Table D-5. Clinical Interest Criteria for ECG Parameters

Parameter	Unit	Actual Value
QTcF	msec	$> 450, > 480, > 500$
QTcF	msec	$30 < \text{Change from Baseline} \leq 60, \text{Change from Baseline} > 60$

Participants will be counted only once for the most severe category. A supportive listing of participants with postbaseline QTcF increases > 30 msec will be provided, including the subject number, study center, and all QTc values (including changes from baseline). A listing of all AEs for participants with postbaseline QTcF increases > 30 msec will also be provided.

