Coagulation Prothrombin time (PT)/INR Other Tests Serum Ethanol Serum Acetaminophen Urine Drugs of Abuse (not including tramadol) Oxycodone Screen Banked Serum Future Testing	Anti-smooth muscle antibody ^b Anti- LC1 ^b	

- a. Mandatory test.
b. Optional test.

Pregnancy Tests (Urine)

Pregnancy testing should not be performed for postmenopausal women.

A urine pregnancy test will be performed at each visit for all female participants of childbearing potential.

More frequent pregnancy tests can be performed throughout the study at the investigator's discretion or if required per local/country requirements.

- If the urine pregnancy test at Screening is negative, then dosing with study drug may begin.
- If the Day 1 or post-baseline urine pregnancy test is positive, dosing with study drug must be withheld.
- For remote visits such as Visit 9 (Follow-up or End of Study) and for women of childbearing potential only, a urine pregnancy test must be performed within 48 hours prior to the remote visits. Investigators/site staff will provide participants with FDA-approved urine pregnancy tests and corresponding written instructions to be used at home by participants for the remote study visits. Sites are required to verbally review testing instructions with all participants.

Clinical Chemistry

A minimum 8-hour fast prior to study drug intake is preferred but not required for blood samples to be drawn for chemistry. If a participant does not fast, the nonfasting status will be recorded in study source documentation.

Urinalysis

Dipstick urinalysis will be completed by the central laboratory at all required visits. Specified abnormal macroscopic urinalyses defined as leukocytes, nitrite, protein, ketones, or blood greater than negative, or glucose greater than normal will be followed up with a microscopic analysis at the central laboratory.

[figure not shown]

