10.3 Analysis of Laboratory Data

Data collected from central laboratories, including additional laboratory testing due to an SAE, will be used in all analyses, except for Baseline where SAE-related laboratory assessments on or before the first dose of study drug will be excluded. The clinical laboratory tests defined in the protocol operations manual (e.g., hematology, clinical chemistry, and urinalysis) will be summarized.

Each laboratory variable will be summarized for all time points (starting with Baseline) with the number of non-missing observations, mean and standard deviation, median, Q1, Q3, minimum and maximum. Mean change from baseline to each applicable post-baseline visit will be summarized, with the number of observations, baseline mean, and visit mean. The change from baseline mean will be presented for the mean change from baseline. In addition, descriptive statistics for values and changes from the baseline values in conventional units at each assessment time point will be presented for selected clinical laboratory parameters listed in [Appendix E](#). A description of reporting the lab values in conventional units in patient narratives (along with the standard reporting in SI units) is presented at the end of [Appendix E](#).

Changes in laboratory parameters will be tabulated using shift tables categorized as low, normal, or high based on the normal ranges of the laboratory used for each sample. A shift table will be provided to summarize shifts from baseline to the final post-baseline value.

Laboratory abnormalities will be evaluated based on Potentially Clinically Significant (PCS) criteria (Appendix Table D-1). For each laboratory PCS criterion, the number and percentage of participants who have a laboratory value meeting the criteria will be summarized. Listings will be provided to summarize participant-level laboratory data for participants meeting PCS criteria.

In addition, ALT, AST, alkaline phosphatase, and total bilirubin will be categorized in Table D-2. The number and percentage of participants meeting each of the criteria for postbaseline hepatic laboratory abnormalities listed in Table D-2 will be summarized. The percentages will be calculated relative to the number of participants with at least 1 available postbaseline assessment. The numerator will be the total number of participants having at least 1 postbaseline value that meets the specific category during the study. A supportive listing will also be provided.

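### The PCS limit for urine specific gravity, 1.1 times the upper limit of normal, lies above any plausible urine value, so the PCS count and listing for this one parameter will be zero whatever the data

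*SAP*

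**What the plan says.** The urinalysis block of SAP Table D-1 (Appendix D) has one entry for specific gravity: "Specific gravity — — $> 1.1 \times ULN". There is no low criterion and no unit. The table's footnote gives the source of the reference limit: "ULN = upper limit of normal value; normal value provided by laboratory". Neither document prints its value, and neither gives another PCS limit or another scale for specific gravity.

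The row will be used. Specific gravity is on the urinalysis panel in section 3.13 of the protocol's Operations Manual, which also says "Dipstick urinalysis will be completed by the central laboratory at all required visits". SAP section 10.3 brings the panel into the analysis: "The clinical laboratory tests defined in the protocol operations manual (e.g., hematology, clinical chemistry, and urinalysis) will be summarized". It then states how the criteria are applied: "For each laboratory PCS criterion, the number and percentage of participants who have a laboratory value meeting the criteria will be summarized". Participants who meet a criterion are also listed.

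The same section provides output that does not depend on the PCS limits. Each laboratory variable gets descriptive statistics at every time point, including the minimum and maximum. In addition, "Changes in laboratory parameters will be tabulated using shift tables categorized as low, normal, or high", using the laboratory's normal ranges, from baseline to the final post-baseline value.

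**The concern.** A multiple of the ULN is a sensible way to mark a large departure when a quantity starts at zero, such as an enzyme activity or a concentration. Specific gravity does not start at zero. Water is 1.000, and everything that distinguishes one urine sample from another lies in the decimals above that. Multiplying the whole value by 1.1 adds at least 0.10 to the limit, which is several times the width of the normal range above water.

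If the limit cannot be crossed, the row reports a structural zero. In most rows of a PCS table a zero means that nobody crossed the limit. Here it would mean only that the limit is out of reach, and the table gives the reader no way to tell the two apart.

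**Working it through.** The plan states no numeric limit for specific gravity, so there is no printed figure to reproduce. The check is whether the rule can be met.

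**Inputs**
- Factor 1.1, applied to the ULN: SAP Table D-1.
- ULN: supplied by the laboratory and not printed. Assumed range 1.020 to 1.050, with 1.000 (water) as the lowest conceivable value.
- Highest specific gravity urine can reach: not in the documents. Assumed 1.035 to 1.050, stretched to 1.080 as a stress test.

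**Step 1: lowest possible limit.** Limit = 1.1 × ULN. With ULN = 1.000, the limit is 1.1 × 1.000 = 1.100. No laboratory range gives a lower one. This already exceeds the stress-test maximum by 1.100 − 1.080 = 0.020.

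**Step 2: limit over the assumed ULN range.** The last column is (1.1 × ULN − 1) / (ULN − 1): how many times the excess over water at the ULN a sample would need in order to reach the limit.

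| Assumed ULN | Limit, 1.1 × ULN | Required excess ÷ excess at ULN |
|---|---|---|
| 1.020 | 1.122 | 0.122 / 0.020 = 6.1 |
| 1.025 | 1.1275 | 0.1275 / 0.025 = 5.1 |
| 1.030 | 1.133 | 0.133 / 0.030 = 4.4 |
| 1.035 | 1.1385 | 0.1385 / 0.035 = 4.0 |
| 1.040 | 1.144 | 0.144 / 0.040 = 3.6 |
| 1.050 | 1.155 | 0.155 / 0.050 = 3.1 |

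**Step 3: reverse check.** For a sample at the highest attainable value to exceed the limit, the ULN must be below (highest value) / 1.1:
- 1.035 / 1.1 = 0.941
- 1.050 / 1.1 = 0.955
- 1.080 / 1.1 = 0.982

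All three are below the value for water, so no real reference range satisfies the condition.

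**Step 4: reporting scale.** If the laboratory reports 1030 instead of 1.030, the limit becomes 1133 and the ratio of value to limit is unchanged. A change of notation does not rescue the rule.

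**The case against.** Four objections deserve an answer.

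*The decisive figures are not in the documents.* This is true of both the ULN and the highest attainable value, so both are declared above as assumptions with ranges. The conclusion does not turn on where in those ranges the truth lies, because the limit cannot fall below 1.10 and the stress-test maximum is 1.080.

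*Other outputs cover the parameter.* This stands, and it sets the size of the point. A reader might infer that high specific gravity would go unseen in this trial. SAP section 10.3 does not support that: the maximum appears at each time point, and a final value above the laboratory range appears as high in the shift table. What is missing is narrower. The shift table uses only the final post-baseline value, so a transient high value mid-study would show only as a by-visit maximum, without a PCS count or listing.

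*Safety is the primary objective, so the primary assessment might seem impaired.* The documents do not support that reading either. Specific gravity is not an adverse event of special interest (SAP Appendix C). Creatinine, blood urea nitrogen, estimated glomerular filtration rate, urine protein and urine glucose have their own PCS criteria. Nor should one predict a specific printed result such as 0 of 75: section 10.3 gives no denominator for the Table D-1 percentages, and 75 is an approximate enrolment target.

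*The factor might be meant for the excess over water.* The SAP does not say so. At an assumed ULN of 1.030 that would give 1 + 1.1 × 0.030 = 1.033, only 0.003 above the ULN, and nothing in the documents supports such a value as potentially clinically significant.

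**Conclusion.** The criterion cannot do its job as written. It is an ill-suited threshold, not a miscalculation, since the SAP computes no figure here. Given that specific gravity is measured relative to water, and assuming that urine does not exceed 1.080, the PCS count and listing for this row are zero by construction under any laboratory range.

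The consequence is minor. One row of the laboratory PCS output is uninformative and could be misread as evidence that no marked values occurred. No safety conclusion in the plan rests on it.

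**What to change.** In SAP Table D-1, replace the specific gravity criterion with an absolute limit, set by the sponsor's safety group from the central laboratory's reference range. The neighbouring urinalysis rows for glucose and protein already use a criterion that is not a multiple of the ULN, and the SAP version history records that those two were updated in version 2.0, so a parameter-specific rule fits the table. If no limit is considered useful, delete the row so that a structural zero is not reported as a PCS result.

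The cost is one table row and the matching line of programming. With a sponsor-set limit, a few concentrated samples may be flagged. Deleting the row loses nothing, because the descriptive statistics and shift table remain.
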